Safety and Adverse Events.....	16
7.1 Definitions.....	16
7.2 Recording of Adverse Events.....	18
7.3 Reporting of Serious Adverse Events and Unanticipated Problems	19
7.3.1 Investigator reporting	19
7.4 Unblinding Procedures.....	21
7.5 Stopping Rules.....	21
7.6 Medical Monitoring	21
7.7 Confidentiality.....	23
7.8 Source Documents.....	24
7.9 Case Report Forms (as applicable)	24
7.10 Records Retention.....	24
Study Monitoring, Auditing, and Inspecting	24
8.1 Study Monitoring Plan.....	24
8.2 Auditing and Inspecting	25
Ethical Considerations	25
Study Finances.....	25
10.1 Funding Source	25
10.2 Conflict of Interest	26

10.3 Subject Stipends or Payments.....	26
Publication Plan	26
Data Management Plan	26
References.....	27
Appendices.....	30
14.1 Appendix 1: Adverse Event Monitoring and Stopping Rules Table.....	30

List of Abbreviations

AE: Adverse Events
cc: cubic centimeters
CRF: case report form
DASS: Depression, Anxiety, and Stress Scale
DCC: data coordinating center
DNA: deoxyribonucleic acid
EC: ethics committee
ELISA: enzyme linked immunosorbent assay
FDA: Food and Drug Administration
g: grams
GFR: glomerular filtration rate
IDS: investigational drug services
IRB: institutional review board
IU: international units
MAR: medication administration record
MCS: mental component score
MSP: severe musculoskeletal pain
MOS: medical outcomes survey
MVC: motor vehicle collision
NRS: numeric rating scale
OT: occupational therapy
PCS: physical component score
PT: physical therapy
PTSD: post-traumatic stress disorder
RCT: Randomized Controlled Trial
RNA: ribonucleic acid
RPS: regional pain scale
SAE: serious adverse events
SF-12: short form 12 item questionnaire
TBSA: total body surface area
UNC: University of North Carolina
UPLC/ESI/MS/MS: Ultraperformance Liquid Chromatography/Electrospray Ionization Mass Spectrometry

Study Summary

Title	Randomized Controlled Trial of Vitamin D to reduce racial disparity in chronic pain following Motor Vehicle Collision
Short Title	VENTURE
IRB Protocol Number	21-2589
Phase	2
Methodology	Double Blind, Randomized Controlled Trial using a parallel design
Study Duration	2 years
Study Center(s)	University of North Carolina-Data Coordinating Center Rhode Island Hospital University of Massachusetts Washington University Cooper University Hospital
Objectives	Assess the feasibility of administering a single dose of Vitamin D in the emergency department to Blacks and Whites presenting within 24 hours of MVC with moderate or severe musculoskeletal pain (MSP), along with the ability of this dose to achieve sustained increases in Vitamin D levels. Evaluate the potential efficacy of this intervention to improve MSP outcomes in Blacks and to reduce MSP disparities in Black vs. White MVC survivors.
Number of Subjects	90
Diagnosis and Main Inclusion Criteria	Presentation to emergency department (ED) within 24 hours of motor vehicle collision with an initial moderate/severe MSP severity (0-10 NRS of ≥ 4)
Study Product, Dose, Route, Regimen	Ergocalciferol (Vitamin D2), 300,000 IU (2-150,000 IU capsules) orally administered once as a single dose prior to discharge from emergency department
Duration of administration	One-time dose
Reference therapy	Matched placebo to Vitamin D preparation

Statistical Methodology	Assess the feasibility of the RCT protocol by (a) calculating recruitment rate and participant retention, and (b) measuring the ability of Vitamin D administration to generate sustained increases in whole-blood Vitamin D concentrations (assessed 3 months after MVC). Assess for preliminary efficacy that Vitamin D administration per protocol (a) decreases overall MSP severity in Black Americans during the 3 months following MVC, and (b) reduced MSP outcome disparities between Black vs. White Americans following MVC.
-------------------------	---

Introduction

This document is a protocol for a human research study. This study is to be conducted according to US and international standards of Good Clinical Practice (FDA Title 21 part 312 and International Conference on Harmonization guidelines), applicable government regulations and Institutional research policies and procedures.

The main objective of this study is to determine whether administration of a single dose of Vitamin D in the Emergency Department following a motor vehicle collision reduces racial disparities in chronic pain following a traumatic event. This phase II, multicenter, randomized controlled trial is a pilot study to determine feasibility and potential efficacy (effect size, sample variation, response to study drug, ability to reduce racial disparity in pain outcomes) that can be used to adequately power a larger randomized controlled trial to fully assess efficacy.

1.1 Background

Motor vehicle collisions (MVCs) are one of the most common traumatic stress exposures in the US, and the most common for which individuals seek emergency department (ED) care. More than 1 million Black Americans (Blacks) come to the ED after MVC each year, and >90% of such ED MVC patients are discharged home with a diagnosis of acute musculoskeletal pain (MSP)/strain only. More than 80% of these individuals report acute moderate or severe (mod/sev) MSP in the ED, and >50% of those with acute mod/sev MSP transition to chronic MSP. MVCs, as well as pain after MVC, disproportionately affect Blacks vs. Whites. For example, in our previous cohort studies 67% of Blacks had mod/sev MSP six months after MVC, vs. only 40% of Whites. Interventions are urgently needed that prevent chronic MSP and reduce these MSP outcome disparities.

One safe, inexpensive, widely available, and well-tolerated intervention, with exciting potential to achieve these goals, is Vitamin D (Vitamin D). Vitamin D insufficiency is much more common in Blacks than Whites. In the investigators' previous observational study, 77% (103/133) of Black MVC survivors had Vitamin D insufficiency at the time of ED evaluation. Such low Vitamin D levels are associated with increased inflammation and worse pain outcomes. Vitamin D has anti-inflammatory, neuroprotective, and analgesic properties, and Vitamin D treatment improves pain outcomes in a range of conditions. Results of a recent Vitamin D intervention study in another trauma population (burn survivors) found that Vitamin D treatment after burn

injury disproportionately improved pain outcomes in Black vs. White burn survivors (67% vs. 33% pain improvement at 6 weeks). Results from a recent analysis suggest that Vitamin D administration in the ED after MVC could prevent at least 70,000 Blacks from developing chronic post-MVC MSP annually.

1.2 Investigational Agents

Some previous treatment trials of Vitamin D have elected to use Cholecalciferol (D3), rather than Ergocalciferol (D2), because of more favorable kinetics.¹ However, both have efficacy in raising serum concentration of 25-hydroxyvitamin D,² and only Ergocalciferol (D2) is available in an FDA-approved prescription formulation that is well-tolerated.^{3,4} In addition, a major benefit of Ergocalciferol (D2) is that a single dose can result in Vitamin D sufficient levels for many weeks/months (Table 1). The dose of Ergocalciferol that we propose, 300,000 IU, has been shown to effectively raise Vitamin D concentration by ~9 ng/ml, and to raise serum 25 hydroxyvitamin D concentration above 30 ng/ml (Vitamin D sufficient *levels*) for over 3 months⁵. The ability of our single-dose protocol to raise Vitamin D will be a primary feasibility endpoint of this pilot study.

Importantly, this dose is extremely well-tolerated: in previous trials, reports of side effects/adverse events is rare,⁶ many studies administering single, high-dose regimens report no side effects⁷⁻⁹, and the most common side effects have been mild GI complaints (e.g. nausea).⁶ Vitamin D administration has also been demonstrated to be safe, even among individuals who are already Vitamin D sufficient.¹⁰⁻¹² Based on the Code of Federal Regulation (CFR), Ergocalciferol will be exempt from an investigational new drug (IND) application.^{5,13-16}

Table 1. Studies demonstrating effectiveness of single-dose Vitamin D (Ergocalciferol, D2) to raise 25-hydroxyvitamin D levels

First author/year	Dose Used	Sample Size	Disease state	Magnitude increases of 25-OH Vitamin D @ timepoint
Martineau et al, 2007 ¹³	100,000 IU (PO)	N=192	Tuberculosis patients	↑ 13 ng/ml @ 6 weeks
Witham, et al, 2012 ¹⁴	100,000 IU (PO)	N=58	Stroke	↑ 6 ng/ml @ 8 weeks
Lanthan et al, 2003 ⁵	300,000 IU (PO)	N=243	Frail elderly	↑ 9 ng/ml @ 12 weeks
Alam, et al, 2017 ¹⁵	600,000 IU PO	N=143	Diabetic neuropathy	↑ 10 ng/ml @ 20 weeks
Cipriani et al, 2013 ¹⁶	600,000 IU PO	N=6	Healthy Volunteers	↑ 6 ng/ml @ 4 weeks

1.3 Clinical Data to Date

Previous studies demonstrate that Vitamin D is a safe, and effective treatment option that has been used to treat a range of painful musculoskeletal disorders. Vitamin D has been shown to reduce chronic pain across a range of painful conditions. Clinical trial results demonstrate that Vitamin D supplementation improves symptoms experienced by patients suffering from fibromyalgia¹⁷⁻²¹, a difficult to treat widespread pain condition. Vitamin D supplementation in a recent clinical trials also improved disability related to low back pain²², osteoarthritis²³ and chronic pain related to migraine headache²⁴. Not all studies are positive, for example a recent study demonstrated that Vitamin D supplementation did not change analgesic consumption, or improve pain outcomes among the general population²⁵; however this study included the general population not those at high risk of chronic pain development as are the individuals we plan to recruit into this study. Taken together, the results of clinical trials of Vitamin D to address painful conditions are promising, and given the lack of available treatment options to prevent chronic pain.

1.4 Dose Rationale and Risk/Benefits

The dose of Ergocalciferol that we propose, 300,000 IU, has been shown to effectively raise Vitamin D concentration by ~9 ng/ml, and to raise serum 25 hydroxyvitamin D concentration above 30 ng/ml (Vitamin D sufficient levels) for over 3 months⁵. The ability of our single-dose protocol to raise Vitamin D will be a primary feasibility endpoint of this pilot study. Importantly, this dose is extremely well-tolerated: in previous trials, reports of side effects/adverse events is rare,⁶ many studies administering single, high-dose regimens report no side effects⁷⁻⁹, and the most common side effects have been mild GI complaints (e.g. nausea).⁶ Vitamin D administration has also been demonstrated to be safe, even among individuals who are already Vitamin D sufficient. ¹⁰⁻¹² Based on the Code of Federal Regulation (CFR), Ergocalciferol will be exempt from an investigational new drug (IND) application.^{5,13-16}

Chronic pain is associated with reduced mental and physical health and interferes with essential activities of daily life. Currently there are limited treatment options to address chronic pain once it has become established and the overarching aim of this clinical trial is to prevent chronic pain development, therefore there is a critical unmet need of safe, non-addictive, non-invasive preventative treatment options that can be administered to MVC survivors in the aftermath of an injury. This study has the potential to benefit participants and future MVC survivors and improve pain and general health outcomes. The risks of taking Vitamin D are small. Side effects from Vitamin D are rare, however, it is possible that over supplementation of Vitamin D may be associated with headache, loss of appetite, dry mouth, metallic taste, and nausea/vomiting.

The risks to the subjects in experiencing these side effects are balanced against the potential for a new, safe, non-opioid preventative treatment option for chronic pain following MVC.

Study Objectives

2.1 Primary Objective:

1. Assess the feasibility of the RCT protocol by (a) calculating recruitment rate and participant retention, and (b) measuring the ability of Vitamin D administration to generate sustained increases in whole-blood Vitamin D concentrations (assessed 3 months after MVC).
2. To demonstrate the preliminary efficacy of Vitamin D administration per protocol on decreasing overall MSP severity during the 3 months following MVC, and reducing MSP outcome disparity between Blacks and Whites following MVC.

2.2 Secondary Objectives:

We will assess the effect of race and sex on treatment outcomes in secondary analyses. This will be accomplished using two analytic strategies. First, a sex X treatment interaction term (secondary analyses) will be entered into our statistical models to assess pain reduction in response to treatment. Second, a stratified analysis will be performed which will examine the influence of both sex and race on treatment effect on primary and secondary outcomes. Further, Secondary stratified analyses evaluate the influence of initial vitamin D level on treatment response. In addition, exploratory analyses on the relationship of vitamin D outcome and trajectory of pain as well as restricting analyses to participants with vitamin D deficiency at baseline will be performed. Secondary analyses will examine treatment effects adjusting for any baseline differences in psychosocial factors between treatment arms.

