3.2 Study Overview

Described the sequence of events in recruiting 90 patients in a multi-center randomized controlled trial. To assess a key primary outcome, we will enroll 50% white and 50% black MVC into the study. Each participant will be screened in based on a point of care Vitamin D test. This will be performed at the time of screening. Individuals with a Vitamin D level <100 ng/ml will be enrolled. Patients will be randomized 1:1 to receive a single dose of 300,000 IU of ergocalciferol versus placebo and followed for 3 months. At 3 months, patients will send a blood sample easily collected at home on a blood spot card to assess Vitamin D level 3 months following injury which is a key feasibility primary outcome.

Patients presenting to the ED within 24 hours of MVC (n=90, 45 non-Hispanic Black, and 45 non-Hispanic White) will receive a single dose of study drug prior to ED discharge (1:1 allocation 300,000 IU ergocalciferol or placebo). Prior to study drug administration, a baseline assessment will be performed (see below), and a fingerstick blood sample will be obtained to evaluate 25-hydroxyvitamin D level. Online survey follow-ups assessing primary and secondary outcomes and potential adverse events will be performed 3 weeks, 6 weeks, and 3 months after ED enrollment by study RAs using web-based REDCap™ software. Participants will also complete brief “flash-surveys” at the 2-week, 4-week, and 5-week timepoints using REDCap survey links. At 3 months, participants will also perform a fingerstick blood collection at home and mail the sample in a prepaid envelope to a lab to be processed to enable assessment of 3 month 25-hydroxyvitamin D concentration by treatment group.

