Analysis plan Overall efficacy (a) will be addressed by evaluating for evidence that Vitamin D administration per protocol vs. placebo decreases overall MSP scores across study timepoints. The effect of the intervention on overall pain over time will be assessed by evaluating the coefficient for treatment group (β_1) in the model: $P_{ij} = \beta_0 + \alpha_{0i} + \beta_1 \text{Treatment}_i + \beta_2 \text{Race}_i + \beta_3 (\text{Treatment} \times \text{Race}) + \varepsilon_{ij}$, where P_{ij} is the pain score for the i th individual at time point j , β 's denotes fixed effects, α_{0i} is the random intercept for the i th individual and ε corresponds to random errors. Narrowing of racial disparity will be addressed by evaluating the interaction between race and treatment (β_3 in model above). Specifically, as described above we will assess whether Vitamin D has greater effect on pain outcomes over time in Blacks than Whites. All analyses will be evaluated on the basis of intention to treat. Prior to

[figure not shown]

Figure 2. Plot demonstrating power to detect a main effect (β_1 , black lines) and interaction (β_3 , blue lines) across a range of sample sizes, at three effect sizes estimated using simulation data generated from previous studies. Vertical red line indicates sample size proposed here (n=90). This demonstrates the power to assess Aim 2a (black) and 2b (blue).

data un-blinding, the study statistician will perform a blind review of the data in which statistical models will be developed and tested using dummy (computer-generated) treatment assignments. This is to ensure important covariates are added to the model prior to un-blinding to eliminate any bias of model covariate selection on results. After un-blinding the data, we will use appropriately specified linear contrasts of model parameters to estimate mean differences between participants treated with Vitamin D and placebo and 95% confidence intervals.

Power Estimates of power were derived using a Monte Carlo simulation based on parameter estimates from our observational data of MVC survivors using R (v. 4.0.2⁴⁸); and the *simr* package (v. 1.0.5⁴⁹). The power across a range of effect sizes for the main effect (a) is shown in Figure 2. These data and analysis must be seen as general estimates given that we lack intervention data for this population/condition.

Secondary Analyses:

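### Baseline Vitamin D is examined as an effect modifier by stratified and subset analyses that do not test it, and no planned model holds treatment x race and treatment x baseline level together

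*Combined protocol and SAP*

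**What the plan says.** Section 2.2 (Secondary Objectives) treats three possible effect modifiers differently.

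- **Sex:** "a sex X treatment interaction term (secondary analyses) will be entered into our statistical models".
- **Baseline Vitamin D:** "Secondary stratified analyses evaluate the influence of initial vitamin D level on treatment response". The next sentence adds, as exploratory work, that "restricting analyses to participants with vitamin D deficiency at baseline will be performed".
- **Race:** handled in section 6.1, where "Narrowing of racial disparity will be addressed by evaluating the interaction between race and treatment". That model contains treatment, race, their product (beta3) and a random intercept.

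Section 6.1 does not return to baseline Vitamin D. No cut-point, number of strata, model or contrast is given for it. Covariates may be added at a blind review ("This is to ensure important covariates are added to the model prior to un-blinding"), but none is named.

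On the link between race and level, section 1.1 says "Vitamin D insufficiency is much more common in Blacks than Whites" and that "77% (103/133) of Black MVC survivors had Vitamin D insufficiency at the time of ED evaluation". It gives no percentage for White patients. Entry is broad: "Individuals with a Vitamin D level <100 ng/ml will be enrolled" (section 3.2).

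**The concern.** Separate estimates within strata, or an estimate in one subset, do not estimate the difference in treatment effect between levels. A reader who compares significance across strata can easily be misled. Cutting a continuous level into groups also discards information.

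The background in section 1.1 strongly implies a mechanism: levels are lower in Black patients, low levels go with worse pain, so supplementation may help Black patients more. If so, a treatment x race interaction could arise wholly or partly from baseline level. No planned model holds both interactions, so the analysis as written does not set one against the other. Sections 1 and 2.3 say the pilot is meant to inform a larger trial, and the source of any differential effect is useful for that.

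**Working it through.** **Inputs from the documents.** Black insufficiency 103/133 (section 1.1); 90 participants, 45 per race, 1:1 allocation (section 3.2); follow-up about 80%, so 0.80 x 90 = 72 (section 6.1).

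**Assumptions.** White insufficiency pW is not given and is varied from 20% to 70%. Effects are in SD units of a patient's mean pain score, because no pain SD is given. Arms are taken as balanced within race and level.

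**Plan's own figure.** 103/133 = 77.4%, which reproduces the stated 77%. So 30/133 = 22.6% of that cohort were not insufficient. The power for beta3 appears only in Figure 2, which is not available here, and was not checked.

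**Step 1: how much of beta3 could be baseline level.** Suppose the treatment effect is a + m x (insufficient), with no separate race effect. The mean effect is a + 0.774m in Black and a + pW x m in White participants. Then beta3 = (0.774 - pW) x m.

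**Step 2: size of the strata.** Section 2.2 does not confine the strata to one race. The sufficient stratum at enrolment is 45 x 0.226 + 45 x (1 - pW).

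**Step 3: information kept by a two-way cut.** For a normal covariate with a linear effect, cut at the pooled insufficient share q = (0.774 + pW)/2, the relative efficiency is f(z_q)^2 / [q(1 - q)], where f is the standard normal density.

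**Step 4: cost of fitting both interactions.** With a binary insufficiency indicator, its correlation with race is r = [(0.774 - pW)/2] / sqrt[q(1 - q)], and the race-interaction SE is multiplied by 1/sqrt(1 - r^2).

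| pW | Share of m in beta3 | Sufficient, of 90 | q | Information kept | r | SE rise |
|---|---|---|---|---|---|---|
| 20% | 57% | 46 | 0.49 | 64% | 0.58 | 22% |
| 30% | 47% | 42 | 0.54 | 64% | 0.48 | 14% |
| 40% | 37% | 37 | 0.59 | 62% | 0.38 | 8% |
| 50% | 27% | 33 | 0.64 | 61% | 0.28 | 4% |
| 60% | 17% | 28 | 0.69 | 58% | 0.19 | 2% |
| 70% | 7% | 24 | 0.74 | 55% | 0.09 | 0.4% |

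**Step 5: what the joint model can detect.** With 72 patients there are 18 per race-by-arm cell. The SE of treatment x race alone is sqrt(4/18) = 0.471, and the effect detectable at 80% power (two-sided 5%) is (1.96 + 0.84) x 0.471 = 1.32 SD. In the joint model this becomes 1.33 to 1.61 SD over the range of pW. The treatment x insufficiency interaction needs 1.43 to 1.61 SD. With all 90 it still needs 1.28 to 1.44 SD.

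**Step 6: how side-by-side strata can mislead.** Let both strata share one true effect, with 72 patients and pW of 30% to 50%. The chance that exactly one stratum is significant is p1(1 - p2) + p2(1 - p1), where p1 and p2 are the powers in the two strata. At pW = 50% and an effect of 0.8 SD, the powers are 0.77 and 0.53, giving 0.48. Over effects of 0.5 and 0.8 SD the chance is 44% to 48%.

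**The case against.** The strongest reply is that the main question is untouched. Objective 2 in section 2.1 asks whether treatment narrows the Black-White difference, and unadjusted beta3 answers that as a total contrast by race, whatever produces it. This stands. Baseline level is an explanatory question, and beta3 should not be replaced.

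Second, the plan is not silent. If the section 6.1 model were refitted in the deficient subset or within strata, beta3 there would be a race interaction at roughly fixed level. That would be coarse evidence on race versus level. But section 2.2 does not say which analyses are restricted, and neither approach estimates the difference in treatment effect between levels. The blind review does not exclude baseline Vitamin D as a covariate, but a main effect alone would not supply the missing interaction.

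Third, a 90-patient pilot cannot settle the matter. This also stands, and it is why the added model should be labelled exploratory.

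Two stronger readings are tempting but unsupported:

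- A reader might infer that race and baseline level overlap too much to be separated. The overlap is partial: about 23% of the earlier Black cohort were not insufficient, and entry is open up to 100 ng/ml. A joint model costs at most about 22% in SE over the assumed range. The obstacle is the unwritten term, with limited precision.
- A reader might apply the 77% to the 45 Black participants and conclude that the sufficient stratum has about 5 per arm. That is a race-by-level cell, which section 2.2 does not name for this analysis. Strata formed across both races would be larger (step 2).

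**Conclusion.** The point holds as a gap in a secondary analysis. The stated methods neither estimate nor test modification by baseline level, and no planned model contains both interactions. How much of beta3 could reflect level depends on a White figure that the documents lack: about 57% of the modification at 20% White insufficiency, 17% at 60%, and less above that. These shares assume that benefit depends only on a binary insufficiency status and that the earlier Black cohort's 77% carries over to this trial.

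This does not invalidate the disparity analysis. Nor do the documents support an inference that the result decides whether the larger trial selects patients on race or on Vitamin D. Section 2.3 describes a trial in high-risk patients that also aims to reduce disparity, without such a rule, and the precision in step 5 could not carry that decision. What remains is a cheap improvement worth making before unblinding.

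**What to change.** In sections 2.2 and 6.1, make the inferential secondary analysis a mixed model with baseline 25(OH)D (continuous, centred) and treatment x baseline 25(OH)D. Fit it alone and jointly with treatment x race.

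- Report beta3 with and without the baseline-level terms, and the baseline-level interaction itself, as estimates with 95% CIs, labelled exploratory.
- Keep unadjusted beta3 as the primary answer on disparity.
- Keep the strata for display, and state their cut-point in advance.
- Name the baseline measurement used. A point-of-care level is required of every participant for eligibility (section 3.6), and sections 3.2 and 5.1 place the fingerstick sample before dosing. Only the additional ED blood draw is optional.

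Cost: two more terms in a secondary model and no new data. The race-interaction SE in the joint model rises by about 0.4% to 22% over the assumed range. Power for the baseline-level interaction is low: about 1.4 to 1.6 SD is needed for 80% power with 72 patients, calculated for a binary insufficiency indicator.

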3.4 Primary Study Endpoints

The primary endpoint of this study will examine the feasibility and efficacy of Vitamin D to improve overall MSP severity outcomes following motor vehicle collision in Blacks and Whites, as well as to reduce MSP outcome disparity between Blacks vs. Whites following MVC.

Outcome to assess feasibility: 90 patients will be enrolled, randomized into one of 2 treatment arms in a 1:1 ratio, and treated with study drug as a single-dose following motor vehicle collision with moderate to severe MSP within a 15-month period. Feasibility will also be measured by the ability to retain >80% of participants through 3-month follow-up, and achieve Vitamin D levels >20 ng/ml in 90% of treatment group at 3-month follow-up. In addition, will determine whether Vitamin D administration per protocol can raise Vitamin D concentration in treatment group >10 ng/ml above baseline. The concentration of Vitamin

D will be calculated before and after the treatment in each treatment arm to assess the response.

Outcome to assess efficacy: Efficacy of Vitamin D will be measured by difference in pain severity in treatment arms versus control arms. Pain reduction between treatment groups will be assessed using patient-reported overall MSP scores (0-10 NRS) obtained at the ED, 3-week, 6-week, and 3-month assessments. Estimates of efficacy will be obtained via repeated measures analysis using mixed effects models. Secondary Study Endpoints

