4.3 Method for Assigning Subjects to Treatment Groups

Once a potential subject has been successfully screened, does not meet any exclusion criteria, is willing to participate in the study, and signs informed consent, the participant will be randomized by the study site using a minimization algorithm stratified on race, sex, and pain score. Randomization of participants using minimization will be accomplished using a centralized, web-based, validated (compliant with FDA 21 CFR Part 11) service (randomize.net). In this algorithm, a new participant is sequentially assigned to a particular treatment group by taking into account the covariates of the current and previously randomized participants. To further optimize power in this small, pilot study to examine the effect of race, and achieve a main goal of this study, a 1:1 ratio of non-Hispanic Black and White Americans will be enrolled. Once enrollment reaches 45 in a given race strata (e.g., non-Hispanic Black), enrollment for that race will cease. All participants, investigators, study

personnel, and follow-up team members will be blinded to allocation and concealment will be maintained throughout the study. Only the investigational pharmacy and study statistician will be unblinded to the drug the participant is receiving. They will not reveal this to the patient care team, investigative team, or to the participant. Dosing schedule, route of administration, number of pills in each dose, and the appearance of the capsules will be identical among each group.

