Similar models as for the primary outcome will be fit for both the Brief Pain Inventory and the SF-12 Mental and Physical Component Scale Scores.

Sex as a biological variable (SABV) will be examined in treatment response including sex-by treatment interaction terms in the mixed effect model specified above and exploring sex differences in therapeutic response to Vitamin D and n-3 PUFAs.

General mental and physical health will be assessed using SF-12 physical and mental component scores (PCS and MCS) and the impact on physical and mental functioning will be determined in each of the treatment groups. A clinically important reduction in SF-12 PCS and MCS ranges between 2.5-4.5⁵⁰; therefore, a reduction of ≥ 4.5 will be considered a clinically significant improvement MCS/PCS.

Brief Pain Inventory: We will also use multivariable analysis to determine the role of n-3 PUFA/Vitamin D supplementation in pain interference using composite and individual measures of the Brief Pain Inventory.

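### Section 2.2 lets observed psychosocial imbalance between the arms choose the covariates of a secondary analysis, outside the pre-un-blinding safeguard of 6.1 and at a cost in precision

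*Combined protocol and SAP*

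**What the plan says.** Section 2.2 (Secondary Objectives) closes with this plan: "Secondary analyses will examine treatment effects adjusting for any baseline differences in psychosocial factors between treatment arms". It does not list the factors, say how a difference is judged, or say when the choice is made.

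Section 6.1, in the analysis plan for the primary mixed model, describes a review before un-blinding in which "statistical models will be developed and tested using dummy (computer-generated) treatment assignments". The stated purpose is "to ensure important covariates are added to the model prior to un-blinding to eliminate any bias of model covariate selection on results".

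The secondary-analysis text that follows in 6.1 does not take up the psychosocial adjustment. Its line "Similar models as for the primary outcome will be fit" refers to the Brief Pain Inventory and SF-12 scores.

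Section 4.3 allocates by a "minimization algorithm stratified on race, sex, and pain score", so the allocation method balances no psychosocial factor. Table 2 (section 5.1) lists the psychosocial scales collected at day 1, before treatment.

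**The concern.** Differences between randomised arms in a variable measured before treatment arise by chance. Choosing covariates by such differences selects them for their relation to treatment assignment. What makes a covariate worth including is its relation to pain, and imbalance says nothing about that. A strongly prognostic scale that happens to be balanced is left out, and a weakly prognostic one that happens to be unbalanced goes in.

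The rule also needs the real allocation. Dummy assignments cannot show which scales differ between the real arms, so the review in 6.1 cannot produce the covariate set that 2.2 asks for. The reason 6.1 gives for settling covariates early applies equally to any adjusted treatment effect, but 2.2 leaves this one unprotected.

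At stake are the precision of the secondary adjusted estimate and confidence in how it was chosen. Section 2.3 intends the data to help design and power a larger trial, so an adjusted effect that depends on an undocumented choice is a poor input.

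**Working it through.** The plan gives no figure on this point, so there is none to reproduce. The text comparison is above; the steps below size the consequences.

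**Inputs**
- Sample size, from 3.4: "90 patients will be enrolled, randomized into one of 2 treatment arms in a 1:1 ratio", so 45 per arm. With the roughly 80% follow-up in 6.1, 0.80 × 90 = 72 are analysed.
- Number of candidate scales, k: not stated. A count of Table 2 at day 1 gives about 10 (catastrophizing, anxiety, depression, anxiety sensitivity, life events, somatic symptoms, global mental health, PTSD symptoms, peritraumatic distress, dissociation). The main range is 8 to 10, with 4 and 12 as extremes.
- Threshold for a difference: not stated. Assumed p < 0.05, with 0.20 as a looser reading.
- Correlation between scales (0 or 0.4), share of outcome variance explained by all scales together (R² 0.2 or 0.4) and treatment effect (0.6 SD): all assumed.

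**Step 1. How often is adjustment triggered by chance?** For independent scales, P(at least one difference) = 1 − (1 − a)^k.

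| k | a = 0.05 | a = 0.20 |
|---|---|---|
| 4 | 18.5% | 59.0% |
| 8 | 33.7% | 83.2% |
| 10 | 40.1% | 89.3% |
| 12 | 46.0% | 93.1% |

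With ten scales correlated at 0.4, simulation gives about 32% at a = 0.05. These figures count how often the covariate set changes. They are not error rates for the treatment effect.

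**Step 2. Does a fixed imbalance rule inflate type I error?** Simulation used a single-outcome analysis of covariance with simple 1:1 randomisation, adjusting for every scale with p < 0.05 between arms. With n = 90 and k = 10, type I error was 4.0% to 4.7%. Over n = 72 and 90 with 8 or 10 scales it was 3.3% to 4.8%. The rule is at or slightly below nominal.

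**Step 3. What precision is lost?** With n = 90, k = 10 and an effect of 0.6 SD:
- no adjustment: power 80% to 81%;
- imbalance-selected covariates: 79% to 84%;
- all ten fixed in advance: 84% to 93%, with type I error 4.7% to 5.5%.

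Imbalance selection therefore gains little over no adjustment. With only three scales fixed in advance, over n = 72 and 90 and 8 or 10 scales, power was about 71% to 92%, against 70% to 85% under imbalance selection.

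The gain from three scales depends on how far they stand in for the rest. Take ten equally weighted scales. If they are independent, three carry 3/10 of the explained variance: 0.06 of total variance at R² = 0.2 and 0.12 at R² = 0.4. If they are correlated at 0.4:
- covariance of the three-scale sum with the ten-scale sum: 3 × (1 + 9 × 0.4) = 13.8;
- variance of the three-scale sum: 3 + 6 × 0.4 = 5.4;
- variance of the ten-scale sum: 10 × 4.6 = 46;
- share carried by the three: 13.8² / (5.4 × 46) = 0.77.

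The gain is small for independent, weakly prognostic scales and larger for correlated, strongly prognostic ones.

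**Step 4. What does the open threshold allow?** Reporting the most favourable of the unadjusted result and the results at imbalance cut-offs of 0.05, 0.10 and 0.20 gave type I error of 6.8% to 10.3% (n = 90, k = 10). Across the settings run, including n = 72, the range is about 6% to 10%.

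**The case against.** The strongest reply is that 2.2 and 6.1 can both be followed. The blind review in 6.1 concerns the primary model. The team could lock that model and then run a separate secondary analysis adjusted for imbalance. This stands. A reader might infer that the two sections contradict each other outright, but 6.1 never says that its covariate rule governs every secondary analysis.

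A reader might also infer that the covariates can be chosen only after full un-blinding. That is too strong. Baseline scales could be compared under coded arm labels, without outcome data and without revealing which arm is active. The documents plan no such step, however, and coded labels still use the real allocation. Section 4.3 adds that "Only the investigational pharmacy and study statistician will be unblinded to the drug the participant is receiving", so the plan does not show that whoever makes the choice would be blind. That is a separate matter, but it gives no reassurance here.

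A third tempting reading is that imbalance-based adjustment invalidates the confidence interval or inflates type I error. Step 2 shows otherwise for a fixed rule. Searching covariate sets for the smallest p-value can give 10% to 15% (n = 72, 6 to 8 candidates), but no section proposes such a search, so that figure does not describe this plan. Even the 6% to 10% in Step 4 requires the threshold to follow the results. The plan permits this by silence but does not propose it.

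Finally, this is a 90-person pilot, the analysis is secondary, and no decision is tied to it. That limits the importance of the point. It does not make selection by imbalance a sound method, and the better method uses data already collected.

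**Conclusion.** The concern holds in a limited form. The covariate rule in 2.2 depends on the real allocation, has no factor list or threshold, and lies outside the principle that 6.1 sets for covariate choice. It does not strictly contradict 6.1, and it leaves the primary treatment and treatment-by-race coefficients untouched.

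The likely cost is precision. A fixed imbalance rule is slightly conservative and recovers little of what prognostic adjustment offers. A lesser risk comes from the open threshold, if it were settled after results are seen.

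All error and power figures rest on assumed correlations, R², effect size and number of scales. They also use simple randomisation and one outcome, where the plan has minimization and a repeated-measures model. They indicate direction and rough size; they do not predict this trial's results.

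**What to change.** In 2.2, replace the sentence with a small set of day-1 psychosocial covariates, chosen for their expected relation to pain, named before un-blinding, and included whatever the observed balance. The Pain Catastrophizing Scale, PROMIS Anxiety and PROMIS Depression are one example. The documents do not rank the scales by prognostic value, so the investigators should justify their choice. State that any further adjustment prompted by observed imbalance is exploratory, and add a line in 6.1 saying that the set is fixed alongside the primary model covariates.

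The cost is a sentence or two and, for three scales, about 3 degrees of freedom. All three are already collected at day 1 (Table 2), so data collection does not change, and neither does the primary model.
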